2.1.2 RELEVANT CLINICAL RESEARCH

Almost all published case series of successful ECPR for OHCA initiate ECPR in the emergency department [Chen 2008, Kagawa 2010, Nagao 2000 and 2010, LeGuen 2011, Morimura 2011, Avali 2012, Bellezzo 2012, Johnson 2014, Sakamoto 2014, Stub 2014]. The reason for this strategy is that the shorter the interval from cardiac arrest onset to initiation of ECPR, the better the chance for a favorable outcome. Figure 3 illustrates this relationship in recent OHCA studies (published after 2010) that specifically reported the collapse to ECPR interval and survival with good neurologic function for the entire study population. These and similar reports are the basis for our initial targeting of a 911 call to ECPR interval <60 min in the EROCA trial. In many countries where ECPR is used to treat OHCA, the ED is routinely staffed by physician specialists in anesthesia or cardiology with more formal training and experience in ECMO than emergency medicine physicians in the U.S. Institutions in the U.S. that perform ECPR for OHCA typically rely on cardiac surgery or cardiology consultants to come to the ED to place ECMO catheters and initiate ECPR [Johnson 2014]. However, the model has many logistical limitations that make it challenging to initiate ECPR within the therapeutic window, and if maintained will be a persistent barrier to widespread implementation.

One example of a program that has incorporated emergency medicine physicians into the ECPR team that includes cardiologist and cardiothoracic surgeons Sharp Memorial Hospital in San Diego [Bellezzo 2012]. In their published case series, 8 out of 18 OHCA patients that met inclusion/exclusion had ECPR successfully initiated in the ED, and 3/18 had spontaneous ROSC before ECPR could be initiation. Of the 8 patients successfully treated with ECPR, 5 survived with good neurologic function (63%). However ECPR catheters could not be placed in 4 patients, and two other patients were reported to have fatal complications of catheter placement (aortic dissection and bifemoral vein cannulation). Although these results demonstrate feasibility in a US ED, they also emphasize the importance of validated training and maintenance of competency for both clinical trial participation and widespread implementation.

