7.3.2 ENROLLMENT/BASELINE

Pre-hospital run sheet(s) will be reviewed for study eligibility and enrollment criteria. The emergency department and hospital electronic medical record will be reviewed for continued inclusion criteria, including time intervals from 911 call to randomization and 911 call to

emergency department admission, if applicable. Until hospital discharge, all data collected will come from previously collected medical records.

Initial Enrollment/Field Baseline (Day 0)

Patients will be enrolled and randomized if they meet the inclusion criteria, namely, the presence of refractory cardiac arrest (defined as no ROSC after initial rhythm analysis and shock if indicated). The treatment group was pre-assigned during the screening phase, but patients with immediate ROSC are considered screened out of the study as no experimental intervention will occur to them.

Patients with persistent cardiac arrest in the field who are randomized will be followed for clinical outcomes per the protocol whether or not they have ECPR.

Due to the sudden and urgent nature of cardiac arrest, treatment must occur immediately. Enrollment will occur at the time of randomization by the prehospital providers at the scene of the out-of-hospital cardiac arrest. Patients will be enrolled under the exception from informed consent (EFIC) process.

Prehospital Medical Records

Prehospital run reports is where Basic Life Support (BLS) and Advanced Life Support (ALS) document the events of the 911 call and often become part of the medical record when patients are brought to the emergency department. Any run reports not found in the medical record and for participants who dies prior to the emergency department will be collected directly from the agencies.

EMS medical records will be reviewed and the following data abstracted:

- Date and time of 911 call
- Time of index cardiac arrest
- Status of witnessed arrest
- Status of Bystander CPR
- Time of collapse
- Time CPR initiated
- Duration of EMS CPR
- Initial recorded cardiac arrest rhythm
- Use of Impedance-threshold device
- Use and type of advanced airway
- Location of cardiac arrest (home, public place, parking lot, street, etc.)
- Date and time of ED arrival

Index Cardiac Arrest/Emergency Department (Day 0)

Emergency Department (ED) medical records will be reviewed and the following data abstracted:

- Date and time of ED arrival
- Status and timing of ROSC
- Demographic information
- Physician progress note(s)

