10.2 STATISTICAL HYPOTHESES

- Co-Primary Endpoint(s): Arrival to qualified ED within 30 minutes

We hypothesize that the proportion of patients randomized to early transport arriving at the hospital within 30 minutes will be greater than the historical proportion of 38.7%.

- Co-Primary Endpoint(s): Initiation of ECPR within 30 minutes of ED arrival

We hypothesize that greater than or equal to 80% of patients will have ECPR (qualifying ED standard care process) initiated within 30 minutes of ED arrival.

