10.3 ANALYSIS DATASETS

The analytic datasets will use a modified per-protocol population. Patients who are assigned to early transport and do not have ROSC after initial rhythm analysis (and shock if indicated) and have the early transport initiated will be considered the primary analytic population for the ED arrival endpoint. Patients who are randomized to early transport and remain in cardiac arrest for at least 10 minutes after ED arrival and have the institutional standard care ECPR process initiated are considered the primary analytic population for the ECPR initiation endpoint. Exploratory clinical and safety endpoints will be collected on the entire population of refractory OHCA patients enrolled/randomized to either early transport or usual care.

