10.4.2 ANALYSIS OF THE PRIMARY EFFICACY ENDPOINT(S)

Co-Primary Endpoint(s): Arrival to qualified ED within 30 minutes

The proportion of qualifying episodes to arrive at the ED within 30 minutes will be compared to our historical data point estimate of 38.7% using a one sample exact test of binomial proportions at the 0.05 two-sided significance level.

Co-Primary Endpoint(s): Initiation of ECPR within 30 minutes of ED arrival

Using the modified intention to treat population with ongoing cardiac arrest in the qualified ED, we will declare the analysis of this objective successful if 80% or more of patients have ECPR (qualifying ED standard care process) initiated within 30 minutes of ED arrival. No formal hypothesis test will be conducted.

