APPENDIX B: UMHS ED ECPR GUIDELINES

Extracorporeal cardiopulmonary resuscitation (ECPR) is standard practice in the University of Michigan Hospital Emergency Department. ECPR utilizes a venous-arterial extracorporeal membrane oxygenation (VA-ECMO) circuit built from several components including. These 510K cleared devices may change based on the institutional practice of the hospital and are provided here as an example of the types of devices used.

QUADROX-iD Adult diffusion membrane Oxygenator
CentriMag Primary Console
CentriMag Back-up Console
CentriMag Motor
CardioHelp System

Inclusion/Exclusion criteria for ECPR

Inclusion Criteria:

- Age 18-70
- -Initial shockable (ventricular tachycardia or ventricular fibrillation) or witnessed pulseless electrical activity or witnessed asystole
- Anticipated interval from cardiac arrest onset (or 911 call) to establishing ECMO flow \leq 60 minutes
- Potentially reversible cause of cardiac arrest ¹

Exclusion Criteria:

[figure not shown]
- Sustained return of spontaneous circulation (ROSC)
- DNAR or DNI advanced directive
- Goals of care exclude ECPR (DNAR/DNI, advanced directive, or family discussion)
- Contraindication to anticoagulation ²
- Estimated BMI >40
- Advanced or life-limiting comorbidity ³
- Unable to independently perform ADLs at baseline
- Treating physician and/or ECMO consultant feels that ECPR is futile ⁴

(1) Potentially reversible causes of cardiac arrest include: ACS, refractory arrhythmia, myocarditis, massive PE, severe hypothermia, drug overdose

(2) Contraindications to anticoagulation include: Suspected or known intracranial hemorrhage, traumatic arrest, significant active bleeding

- (3) Advanced or life-limiting co-morbidities include: Stroke or CNS lesion with significant neurologic or cognitive impairment, liver cirrhosis including ESLD, ESRD, advanced COPD or other chronic lung disease, advanced or metastatic malignancy
- (4) Indications of futility are subject to the gestalt of the treating physician and/or ECMO surgeon, but may include: Septic shock multiorgan failure, hypoxemic arrest, metabolic acidosis with pH <7.0, Lactate >15, ETCO₂ <10 despite optimal ACLS, poor candidate for destination LVAD, artificial heart, or transplant

UMHS AES ECPR Protocol

- (1) Inclusion/Exclusion criteria per Appendix 1

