- (2) Necessary resources will be determined case-by-case, with necessary available resources including: ECMO specialist or ECMO credentialed emergency department RN dedicated to sitting pump until transfer to CVC; CVC bed to be made available ASAP; ED and EC3 staffing/volume/capacity to care for ECPR patient; Availability of EC3 Intensivist by phone or in person

- (3) Initiation of ECPR includes femoral veno-arterial cannulation by an ECMO surgeon or an emergency physician credentialed for the procedure, as well as circuit and pump management by an ECMO specialist or ECMO-credentialed emergency department RN
- (4) Potential disposition destinations include: Cardiovascular center ICU; cardiac catheterization lab; and/or EC3, if EC3 intensivist and ECMO credentialed RN available

Standard data collected on cardiac arrest patients in UMHS AES

For internal review, quality improvement, and education, the following data elements are among those routinely obtained in patients with cardiac arrest and post-cardiac arrest care delivered in AES:

1. Time intervals, including time of arrest or 911 call, transport time, time of ED arrival, down-time, duration of CPR, time of return of circulation or initiation of ECPR
2. Drugs and shocks administered
3. Method(s) and device(s) used for CPR
4. Method(s) and device(s) used for airway management
5. End-Tidal CO2 measurements
6. Vital sign trends, with attention to diastolic blood pressure measurements when obtained invasively
7. Ventilator parameters, including settings and dynamic measurements
8. Blood gas results
9. Cerebral blood flow index via "C-Flow" device
10. Method(s) of therapeutic hypothermia, when utilized
11. Initial and subsequent cardiac rhythms
12. Return of circulation ECG interpretations
13. Bedside echocardiography images and interpretations
14. Cardiac catheterization results
15. ED, ICU, and hospital length of stay
16. EEG and neuro-prognostication results, including head CT, MRI, SSEP, NSE level, Neurology consultation documentation
17. Cerebral performance category upon discharge

Cardiac Arrest – General

This protocol should be followed for all adult cardiac arrests. Medical cardiac arrest patients undergoing attempted resuscitation should not be transported unless return of spontaneous circulation (ROSC) is achieved or transport is ordered by medical control or otherwise specified in protocol.

- ☑ If an arrest is of a known traumatic origin refer to the **Dead on Scene Protocol**.

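### Sections 10.3 and 10.4.2 give the ECPR co-primary different denominators for one untested 80% rule, and the 10.3 set is conditioned on something close to the outcome

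*Combined protocol and SAP*

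**What the plan says.** Section 10.2 hypothesises that at least "80% of patients will have ECPR (qualifying ED standard care process) initiated within 30 minutes of ED arrival". It does not say which patients form the denominator.

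Section 10.3 calls its datasets modified per-protocol. For this endpoint it takes early-transport patients who remain in arrest for at least 10 minutes after ED arrival and who "have the institutional standard care ECPR process initiated are considered the primary analytic population for the ECPR initiation endpoint".

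Section 10.4.2 states the success rule, an observed proportion of 80% or more with no formal test, and introduces it with "Using the modified intention to treat population with ongoing cardiac arrest in the qualified ED". It states neither the 10-minute condition nor the process condition, and the population it names is not defined elsewhere. The objectives in the Précis and Section 3 likewise refer to patients in ongoing refractory arrest, without either condition. Section 2.2 points to a third group: all patients who meet the criteria for ECPR.

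**The concern.** Because success is a bare proportion against a cut-off, the denominator decides the verdict. Two denominators stand in the current text under opposing labels, and no cross-reference connects them. If both remain, the choice could be made once the data are known.

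The 10.3 entry condition is also close to the outcome. The endpoint is ECPR initiated by 30 minutes, and entry requires the ECPR process to have been initiated. A patient in ongoing arrest for whom nothing is started is a plain failure of a rule about timely starts, yet under 10.3 that patient leaves the calculation. Such patients are foreseeable. Appendix B has ECPR exclusions that Section 5.2 does not list as trial exclusions, among them estimated BMI above 40, life-limiting comorbidity, and "Treating physician and/or ECMO consultant feels that ECPR is futile". The co-primary is meant to establish feasibility before a larger trial, so a pass that depends on the choice of denominator would mislead that decision.

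**Working it through.** The plan gives no power or precision figure for this co-primary. The 98% in Section 10.5 belongs to ED arrival. It reproduces (exact test against 38.7%, n = 24, upper critical value 15, power 98.3% at 19/24) but does not bear on this point.

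**1. The two sets side by side**

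| | Section 10.3 | Section 10.4.2 |
|---|---|---|
| Label | modified per-protocol | modified intention to treat |
| Arrest | at least 10 minutes after ED arrival | ongoing in the qualified ED, no duration |
| ECPR process | must have been initiated | not mentioned |
| Success rule | none stated | observed 80% or more, no test |

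**2. What the process condition can mean.** If it means that ECPR started, every patient in the set received ECPR and only a late start can fail. If it means that the pathway was activated, activated patients who never receive ECPR stay in as failures, but patients never activated drop out. Appendix B says that "Initiation of ECPR includes femoral veno-arterial cannulation by an ECMO surgeon or an emergency physician credentialed for the procedure", which does not settle where a failed cannulation falls.

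**3. Formula.** Let N be the early-transport patients in ongoing arrest in the ED, k those outside the 10.3 set, and t those with timely ECPR. If every timely patient lies in the 10.3 set, 10.3 gives t/(N − k) and 10.4.2 gives t/N. The first is never smaller, so 10.3 is the easier rule. The exception would be ECPR started before minute 10.

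**4. Illustration (assumed counts).** 15 in arrest at 10 minutes = 11 timely + 1 late + 1 failed cannulation + 2 never activated. Exact (Clopper-Pearson) 95% CIs in brackets.

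- 10.3, ECPR started: 11/(11 + 1) = 11/12 = 92% (62 to 99.8%), pass.
- 10.3, pathway activated: 11/(11 + 1 + 1) = 11/13 = 85% (55 to 98%), pass.
- 10.4.2: 11/15 = 73% (45 to 92%), fail.

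If all 15 were activated, the activation reading would also give 11/15 and would not split from 10.4.2.

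**5. How few patients suffice.** For N from 10 to 24, the smallest k at which the verdicts can differ is 1, except 2 at N = 10, 15 and 20. At N = 16 and k = 1, 12/15 = 80% passes and 12/16 = 75% fails. The ongoing-arrest rule cannot pass at all once k exceeds 0.2N: k = 3 for N = 10 to 14, 4 for 15 to 19, and 5 for 20 to 24.

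**6. Chance of a split (assumed inputs).** Let f be the share of N in the 10.3 set and q the timely share of those. Draw m from Binomial(N, f) and t from Binomial(m, q), then compare t/m and t/N with 80%. For N = 20 and q = 0.9:

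| f | Pass 10.3 | Pass 10.4.2 | Pass 10.3 only |
|---|---|---|---|
| 0.7 | 89.5% | 8.6% | 80.9% |
| 0.9 | 91.0% | 67.3% | 23.7% |
| 1.0 | 95.7% | 95.7% | 0% |

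**7. An outside illustration.** The case series in Section 2.1.2 reports that "8 out of 18 OHCA patients that met inclusion/exclusion had ECPR successfully initiated in the ED, and 3/18 had spontaneous ROSC" before ECPR, and that "ECPR catheters could not be placed in 4 patients, and two other patients were reported to have fatal complications of catheter placement". No times are given, so these are upper limits on the timely share: 8/8 = 100% among those started; 8/(8 + 4 + 2) = 8/14 = 57% among those with the process begun (8/12 = 67% if the two fatal complications are among the 8); and 8/(18 − 3) = 8/15 = 53% in ongoing arrest.

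**The case against.** The strongest reply is that 10.3 is the datasets section and expressly designates the primary population, so 10.4.2 is loose shorthand for it. That is possible, but the labels oppose each other and nothing links them. It would not rescue the rule either: following 10.3 still removes never-started patients, contrary to the objectives.

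A second reply is that Section 4.2.1 defines the endpoint as a time interval, which exists only where ECPR starts. A responder rule does not need the interval, since a patient without ECPR at 30 minutes can be counted as not met. Section 6, the reference to flow in 4.2.1 and the separate catheter and initiation times in 7.3.2 do help to identify the endpoint event, and they make a failed cannulation look like no initiation. They do not define the process condition in 10.3.

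Third, limiting the analysis to ECPR candidates is defensible given Section 2.2. That stands, but eligibility is not the same condition as initiation.

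Two stronger readings go too far. A reader might infer from Section 7.3.2 that the plan itself expects ED patients in ongoing arrest without ECPR, because patients "will be followed for clinical outcomes per the protocol whether or not they have ECPR". That sentence covers all randomized patients with persistent field arrest, usual care included, and forecasts nothing about this group. A reader might also infer that the documents require every ongoing-arrest patient, including those ineligible for ECPR, to count in the primary set. Section 2.2 leaves that open.

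The stakes are those of a pilot, and the individual data tables in 10.4.10 would let readers recalculate. They would not show which verdict was prespecified.

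**Conclusion.** The concern holds. Sections 10.3 and 10.4.2 define different denominators for the same untested 80% rule, and the 10.3 set rests on an undefined condition that nearly repeats the endpoint. This is an inconsistency in a co-primary analysis and should be corrected before any data are seen.

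One or two patients outside the 10.3 set are enough to make opposite verdicts possible for any N from 10 to 24, and the disagreement runs essentially toward an easier pass under 10.3. How likely a split is cannot be read from the documents: the 15-patient counts and the values of N, f and q are assumptions, and no split arises if every patient in ongoing arrest meets the 10.3 conditions. The case series is another programme, has no 10-minute rule, and its stated outcomes cover at most 8 + 3 + 4 + 2 = 17 of 18 patients, so it illustrates the mechanism and is not a forecast.

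**What to change.** Name one population for the 80% rule and use it in both 10.3 and 10.4.2, fixed before the data are seen and not conditioned on ECPR or its process having been started. The ongoing-arrest set of 10.4.2 and the objectives is the default. If the sponsor intends the ECPR-eligible group of Section 2.2, define it by eligibility criteria, naming the version used, and not by initiation.

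- Count patients in the chosen set without ECPR by 30 minutes as not meeting the endpoint.
- State whether the 10-minute condition is kept.
- State how ROSC in the ED before ECPR counts for this endpoint, consistently with 5.3 and 10.4.1. Both include such patients in the primary analysis but name no endpoint.
- Report the other set, and the process-initiated set with that term defined, as supportive proportions with exact confidence intervals.

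For the ongoing-arrest set the cost is wording: ED arrival, ROSC timing and time of ECPR initiation are already abstracted under 7.3.2. ECPR eligibility and pathway activation time are not listed there and may each need one added field, although physician notes and procedure outcomes are collected and may supply reasons for not starting. The downside is that the primary proportion may be lower, because on the default set patients ineligible for ECPR count as not met. The supportive figure in eligible patients shows how much of the shortfall that explains.

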10.4 DESCRIPTION OF STATISTICAL METHODS

10.4.1 GENERAL APPROACH

The primary goal of this study is to establish that a high proportion of patients with refractory OHCA can be expeditiously transported to the hospital for initiation of advanced resuscitation. Randomization is not intended to create comparable groups, but instead is being used to demonstrate the feasibility of using a position sensitive randomization procedure in the field. Randomization in this protocol includes two currently used approaches to OHCA: expedited transport to the hospital after initial attempts at resuscitation versus continued resuscitation efforts in the field until ROSC.

Descriptive statistics for study groups will be presented as medians, and interquartile ranges for continuous data; categorical data will be reported as proportions.

Patients randomized to the test arm and achieve ROSC prior to initiation of ECPR will be included in the primary analysis of the expedited transport group.

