3 OBJECTIVES AND PURPOSE

Co-Primary: To determine what proportion of patients with refractory OHCA can be delivered to an ECPR-capable ED within 30 min of the 911 call or prehospital provider witnessed first cardiac arrest (qualifying OHCA event). This is to establish the feasibility of the early transport protocol.

Co-Primary: To determine what proportion of patients can have ECPR initiated within 30 minutes of ED arrival for patients with ongoing refractory OHCA. This is to establish the feasibility of the ED advanced resuscitation protocol in situations where prenotification of the team has occurred by qualified prehospital providers.

Safety: To estimate frequency of adverse events associated with study interventions. This early phase trial is not adequately sized to provide meaningful comparative estimates. The

population of OHCA survivors is at high risk for death and adverse experiences under routine clinical care.

Exploratory: Demonstrate the feasibility of field randomization of patients with refractory OHCA. This study is using a novel procedure to determine eligibility based on timing and location.

Exploratory: We will collect ECPR process measures including time to confirmed vascular access and confirmed ECPR cannulation. These measures are collected as part of routine clinical care on all patients undergoing ECPR for cardiac arrest at the qualified emergency department(s).

Exploratory: To provide preliminary estimates regarding neurological outcomes following this treatment. This study is not adequately sized to provide meaningful comparative data on neurological outcomes. This aim will provide insight into the proportion of patients with excellent outcomes, along with the proportion of patients with neurologically unsatisfactory outcomes.

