5.3 STRATEGIES FOR RECRUITMENT AND RETENTION

There is no participant “recruitment” for this study as it is not possible to prospectively identify victims of out-of-hospital sudden cardiac arrest and obtain informed consent. Participants will be included in the study if they meet enrollment criteria at the time of their cardiac arrest. Based on historical data, we anticipate randomizing 30 refractory OHCA patients over 18 months. This clinical trial will be conducted under exception from informed consent (further details in Section 13).

Patients will be screened and assigned a randomization group at the time of dispatch. Study eligibility and randomization will be further determined with the aid of an algorithm or expected time to eligible hospital map where a 911 dispatch operator will input eligibility data points and receive one of 3 responses. This is pre-enrollment treatment group assignment. Despite assignment to one of these three groups, the patient will not be considered randomized until they have met the inclusion criteria (including the refractory nature of the cardiac arrest.)

1. Not eligible continue usual resuscitative care (stay in place until ROSC or resuscitation

meets termination criteria)

2. Eligible, randomized to usual care (operationally same as 1 for paramedics)
3. Eligible, randomized to early transport

After an initial rhythm assessment and shock delivery (if indicated), patients who do not have ROSC will be considered randomized. Based on the assignment given at the time the prehospital providers were dispatched, they will either continue usual care (stay in place until ROSC) if assigned to that group (control), or undergo expedited transport with mechanical CPR device in place (experimental group). Patients who do not meet inclusion criteria or have exclusion criteria will not be considered randomized or enrolled, since no experimental procedures will occur to them (standard procedure is for patients to be transported after ROSC). If ROSC is achieved during transport or in the emergency department (experimental group), they will be included in the primary analysis of the expedited transport group. All patients will be followed for clinical outcomes.

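### The ECPR-within-30-minutes co-primary has no single denominator: Sections 10.3, 10.4.1, 10.4.2 and 5.3 treat patients with ROSC before ECPR differently, and the 80% rule can turn on which is followed

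*Combined protocol and SAP*

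**What the plan says.** The objective in Section 3, like the synopsis, concerns patients still in arrest: "ECPR initiated within 30 minutes of ED arrival for patients with ongoing refractory OHCA".

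Four later sections bear on who is counted:

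- **Section 10.3** announces the population type: "The analytic datasets will use a modified per-protocol population". For the ECPR endpoint it takes early-transport patients who "remain in cardiac arrest for at least 10 minutes after ED arrival and have the institutional standard care ECPR process initiated".
- **Section 10.4.2** opens the ECPR analysis differently: "Using the modified intention to treat population with ongoing cardiac arrest in the qualified ED". It repeats neither the 10-minute condition nor the process-started condition.
- **Section 10.4.1** says that test-arm patients who "achieve ROSC prior to initiation of ECPR will be included in the primary analysis of the expedited transport group". No co-primary is named.
- **Section 5.3** reads: "If ROSC is achieved during transport or in the emergency department (experimental group), they will be included in the primary analysis". Again no co-primary is named.

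The decision rule in Section 10.4.2 is a point estimate: "we will declare the analysis of this objective successful if 80% or more of patients have ECPR" within 30 minutes of ED arrival. It adds: "No formal hypothesis test will be conducted".

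**The concern.** The same patient can be in or out of the ECPR denominator depending on which section the analyst follows. The patients affected are those who regain a pulse in transport or in the ED before ECPR. They no longer need the procedure, and Appendix B lists sustained ROSC as an exclusion for it. Once in the denominator they therefore count as non-successes unless they re-arrest, although the objective is about how quickly the ED starts ECPR in continuing arrest.

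With a fixed threshold, a small denominator and no interval or test, a few such patients can decide whether the co-primary is declared met. The trial is unblinded (Section 10.6.2), so a denominator left open could be settled after the results are known.

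**Working it through.** **1. The plan's own figure.** The only power figure, 98% in Section 10.5, belongs to the ED-arrival co-primary. With n = 24 and a null of 38.7%, the exact two-sided 0.05 test rejects upward at 15 or more: P(X ≥ 15) = 0.0156, while P(X ≥ 14) = 0.040 exceeds 0.025. Power at 19/24 is 0.983, so the figure reproduces. No corresponding figure is given for the ECPR co-primary.

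**2. The sections side by side** (early-transport patients who reach the ED).

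| Patient | 10.3 | 10.4.2 | 10.4.1 / 5.3, literal |
|---|---|---|---|
| ROSC in transport | out | out | in |
| ROSC at ED minute 5 | out | not determined | in |
| ROSC at minute 15, process already started | in, scoring not stated | not determined | in, scoring not stated |
| In arrest past minute 10, process never started | out | in | not addressed |

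**3. Room under the 80% rule.** Successes needed = 0.8N, rounded up.

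| N | Needed | Misses allowed |
|---|---|---|
| 10 | 8 | 2 |
| 12 | 10 | 2 |
| 15 | 12 | 3 |
| 20 | 16 | 4 |
| 24 | 20 | 4 |

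N = 24 is an upper bound: Section 10.5 expects the protocol to be used on at least 24 of 30. The number who will qualify for the ECPR endpoint is not given.

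**4. Can the reading change the result?** Two cases with 24 patients, 4 of them with ROSC (24 × 3/18):

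- 19 timely: 19/20 = 95.0% with ROSC excluded (met); 19/24 = 79.2% included (not met).
- 20 timely: 20/20 = 100% excluded; 20/24 = 83.3% included (met both ways).

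If more than 20% have ROSC, the included version fails even when every other patient is timely (5 of 24: 19/24 = 79.2%).

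**5. How likely is that?** Let p be the timely rate in persistent arrest and r the share with ROSC before ECPR.

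- Included: P(Bin(N, p(1 − r)) ≥ 0.8N).
- Excluded: the number with ROSC, k, is Bin(N, r) and the denominator shrinks to N − k. Sum over k of P(k) × P(Bin(N − k, p) ≥ 0.8(N − k)).

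The value of p is an assumption. The 3/18 = 16.7% comes from the US ED series cited in Section 2.1.2 and means ROSC at any time before ECPR.

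| N | p | r | Excluded | Included |
|---|---|---|---|---|
| 12 | 0.90 | 16.7% | 0.877 | 0.391 |
| 10 | 0.90 | 16.7% | 0.830 | 0.526 |
| 12 | 0.90 | 10% | 0.895 | 0.594 |
| 12 | 0.90 | 5% | 0.898 | 0.753 |
| 12 | 0.80 | 16.7% | 0.582 | 0.181 |
| 12 | 0.95 | 16.7% | 0.970 | 0.529 |

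**The case against.** The best defence is that the specific section governs the general one. Section 10.3 defines a separate population for each co-primary, and the sentences in 10.4.1 and 5.3 may be meant for ED arrival; Section 5.3 covers ROSC in transport, before any ED clock starts. This is a reasonable reading, but the text does not state it, and 10.4.1 ties its rule to ECPR initiation, the event of the other endpoint. Even if accepted, it leaves 10.3 and 10.4.2 with different names and conditions.

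Four stronger readings are tempting and are not supported:

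- *Patients with ROSC after minute 10 are scored as failures and can never be successes.* No section states their scoring. Appendix B excludes only sustained ROSC, so re-arrest could still lead to ECPR. Sections 10.2 and 10.4.2 also add a parenthesis about the ED's standard process to the success criterion. If process start is what counts, a start at minute 12 followed by ROSC at minute 15 is a success. Section 4.2.1 speaks of ECPR flow, so the point is open.
- *The cited series shows the conclusion changing.* It does not. ECPR was initiated in 8 of 18: 8/15 = 53% with ROSC excluded and 8/18 = 44% included, below 80% either way.
- *The 17% rate applies after minute 10.* The series has no such landmark, and the documents give no rate for that window. The large differences therefore describe the literal reading of 10.4.1 and 5.3. Also, holding the denominator at 10 on both sides would give 93% against 53%; once exclusion shrinks it, the comparison is 83% against 53%.
- *The remedy is simply to drop everyone with ROSC between minutes 10 and 30.* That conditions on what happens after the landmark. A slow team leaves more time for ROSC, and its slow cases would then leave the denominator.

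It is also fair that this is a feasibility pilot and that individual primary-endpoint data will be tabulated (Section 10.4.10), so another denominator could be recovered afterwards. That helps readers but does not prespecify the declared result.

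**Conclusion.** Wrong as written. The inconsistency in the denominator is in the text and needs no assumption. Its size does. For 12 patients with 90% timely initiation, the chance of meeting the rule is about 88% against 39% if ROSC before ECPR occurs as often as in the cited series, and about 90% against 75% to 59% if it occurs in 5% to 10%. The timely rate, the number of patients and the ROSC rate are all assumed. A different conclusion is possible, not certain. The documents do not support saying that the plan counts every ROSC in the ED as a failure; they leave that undecided.

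**What to change.** 1. Use the Section 10.3 landmark population for the ECPR co-primary in Section 10.4.2 as well, with the same conditions and one population name.
2. State in Sections 10.4.1 and 5.3 that the inclusion of patients with ROSC applies to the ED-arrival co-primary only.
3. State whether success means ECPR flow or start of the ECPR process. Define the process-started condition in 10.3 separately from success; if it means ECPR itself was begun, the denominator depends on the outcome.
4. State how sustained ROSC after minute 10 but before ECPR is scored. List these patients separately and report the 80% result both with and without them, naming in advance which version decides. Neither is neutral: excluding them can favour slow initiation, and including them can count recovery as a miss.

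The cost is wording in four sections and one extra table line. Section 7.3.2 already has ROSC status and timing, and the time of ECPR initiation, abstracted from ED records. No new data and no change in care are needed.
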